9.11 Progression/relapse

Relapse/progression will be determined as per Cheson 1999 criteria (see Appendix 8 “Response criteria for lymphoma”)

Progressive disease should be based on CT scan and not PET or MRD.

A pathological confirmation by biopsy of the lesion should be done if possible.

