20.8 Appendix 8: Response criteria for lymphoma – Cheson 1999

Complete Response (CR)

A complete response requires the following:

- Complete disappearance of all detectable clinical and radiographic evidence of disease and disappearance of all disease-related symptoms if present before therapy, and normalization of those biochemical abnormalities [e.g., lactate dehydrogenase (LDH)] definitely assignable to NHL
- All lymph nodes and nodal masses must have regressed to normal size (≤ 1.5 cm in their greatest transverse diameter for nodes > 1.5 cm before therapy). Previously involved nodes that were 1.1 to 1.5 cm in their greatest transverse diameter before treatment must have decreased to ≤ 1 cm in their greatest transverse diameter after treatment, or by more than 75% in the sum of the products of the greatest diameters (SPD).
- The spleen, if considered to be enlarged before therapy on the basis of a CT scan, must have regressed in size and must not be palpable on physical examination. Similarly, other organs considered to be enlarged before therapy due to involvement by lymphoma, such as liver and kidneys, must have decreased in size.
- Bone marrow, if positive at baseline, must be histologically negative for lymphoma.

Complete Response, unconfirmed (CRu)

CRu includes those patients who fulfil criteria 1 and 3 above, but with one or more of the following features:

- A residual lymph node mass greater than 1.5 cm in greatest transverse diameter that has regressed by more than 75% in the SPD. Individual nodes that were previously confluent must have regressed by more than 75% in their SPD compared with the size of the original mass.
- Indeterminate bone marrow (increased number or size of aggregates without cytologic or architectural atypia).

Partial Response (PR)

A partial response requires the following:

- $\geq 50\%$ decrease in SPD of the six largest dominant nodes or nodal masses. These nodes or masses should be selected according to the following features: (a) they should be clearly measurable in at least two perpendicular dimensions, (b) they should be from as disparate regions of the body as possible, and (c) they should include mediastinal and retroperitoneal areas of disease whenever these sites are involved.

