## 4.5 General statistical approach

### 4.5.1 Statistical analysis

Continuous data will be summarized in tables displaying number of observations, mean, standard deviation, median, range; quartiles will also be presented when considered relevant.

Categorical data will be expressed as frequencies and percentages (of non-missing data).

Response rates (according to Cheson 1999 or MRD) will be expressed with 90% confidence limits (to be consistent with one sided 5% level of significance) according to Pearson-Clopper method. The number and percent of patients falling into each category of response will be provided.

Time to event will be performed using Kaplan-Meier method. Survival probabilities, median survival and quartiles will be estimated with their 95% CI. Survival curves will be provided. A dedicated analysis on survival (PFS/OS) will be performed in order to determine baseline prognostic factors. The implemented method will take into account the specificities of on-demand treatment during the second maintenance period.

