### 5.7.4 Response rate

Table 5.7-6 Response according to Cheson 99 – Efficacy Set

		Evaluation after 3 years of maintenance N=XX	End of treatment N=XX
Response (Cheson 99)			
Complete Metabolic Response		XX (XX.X%)	XX (XX.X%)
Partial Metabolic Response		XX (XX.X%)	XX (XX.X%)
No Metabolic Response		XX (XX.X%)	XX (XX.X%)
Progressive Metabolic Disease		XX (XX.X%)	XX (XX.X%)
Not Evaluated		XX (XX.X%)	XX (XX.X%)
Overall Response Rate (ORR)			
Patients with ORR		XX (XX.X%)	XX (XX.X%)
IC 95%		[XX.X% - XX.X%]	[XX.X% - XX.X%]
Overall Response Rate* (ORR)			
Patients with ORR		XX (XX.X%)	XX (XX.X%)
IC 95%		[XX.X% - XX.X%]	[XX.X% - XX.X%]

\* Patients who relapsed or died during treatment phase are considered as non-responders even if they were responders before withdrawal.

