**Table 5.7-2 Response according to Cheson 99 – Safety Set**

	Evaluation after 3 years of maintenance N=XX	End of treatment N=XX
Response (Cheson 99)		
Complete Metabolic Response	XX (XX.X%)	XX (XX.X%)
Partial Metabolic Response	XX (XX.X%)	XX (XX.X%)
No Metabolic Response	XX (XX.X%)	XX (XX.X%)
Progressive Metabolic Disease	XX (XX.X%)	XX (XX.X%)
Not Evaluated	XX (XX.X%)	XX (XX.X%)
Overall Response Rate (ORR)		
Patients with ORR	XX (XX.X%)	XX (XX.X%)
IC 95%	[XX.X% - XX.X%]	[XX.X% - XX.X%]
Overall Response Rate* (ORR)		
Patients with ORR	XX (XX.X%)	XX (XX.X%)
IC 95%	[XX.X% - XX.X%]	[XX.X% - XX.X%]

\* Patients who relapsed or died during treatment phase are considered as non-responders even if they were responders before withdrawal.

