## 7.5 Appendix C: Response Criteria for Lymphoma – Lugano Classification

Bruce D. Cheson, Richard I. Fisher, Sally F. Barrington, Franco Cavalli, Lawrence H. Schwartz, Emanuele Zucca, and T. Andrew Lister. *J Clin Oncol* 2014;32(27):3059-68.

Revised Criteria for Response Assessment		
Response and Site	PET-CT-Based Response	CT-Based Response
Complete	Complete metabolic response	Complete radiologic response (all of the following)
Lymph nodes and extralymphatic sites	Score 1, 2, or 3 with or without a residual mass on 5 Point Scale†  It is recognized that in Waldeyer's ring or extranodal sites with high physiologic uptake or with activation within spleen or marrow (eg, with chemotherapy or myeloid colony-stimulating factors), uptake may be greater than normal mediastinum and/or liver. In this circumstance, complete metabolic response may be inferred if uptake at sites of initial involvement is no greater than surrounding normal tissue even if the tissue has high physiologic uptake	Target nodes/nodal masses must regress to $\leq 1.5$ cm in LD  No extralymphatic sites of disease
Nonmeasured lesion	Not applicable	Not applicable
Organ enlargement	Not applicable	Rgress to normal
New lesions	None	None
Bone marrow	No evidence of FDG-avid disease in marrow	Normal by morphology; if indeterminate, IHC negative

Partial	Partial metabolic response	Partial remission (all of the following)
Lymph nodes and extralymphatic sites	Score 4 or 5† with reduced uptake compared with baseline and residual mass(es) of any size At interim, these findings suggest responding disease At end of treatment, these findings indicate residual disease	≥ 50% decrease in SPD of up to 6 target measurable nodes and extranodal sites When a lesion is too small to measure on CT, assign 5 mm x 5 mm as the default value When no longer visible, 0 x 0 mm For a node > 5 mm x 5 mm, but smaller than normal, use actual measurement for calculation
Nonmeasured lesion	Not applicable	Absent/normal, regressed, but no increase
Organ enlargement	Not applicable	Spleen must have regressed by > 50% in length beyond normal
New lesions	None	None

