Bone marrow	Residual uptake higher than uptake in normal marrow but reduced compared with baseline (diffuse uptake compatible with reactive changes from chemotherapy allowed). If there are persistent focal changes in the marrow in the context of a nodal response, consideration should be given to further evaluation with MRI or biopsy or an interval scan	Not Applicable
No Response or stable disease	No metabolic response	Stable Disease
Target nodes/nodal masses, extranodal lesions	Score 4 or 5 with no significant change in FDG uptake from baseline at interim or end of treatment	< 50% decrease from baseline in SPD of up to 6 dominant, measurable nodes and extranodal sites; no criteria for progressive disease are met
Nonmeasured lesion	Not applicable	No increase consistent with progression
Organ enlargement	Not applicable	No increase consistent with progression
New lesions	None	None
Bone marrow	No change from baseline	Not applicable
Progressive disease	Progressive Metabolic Response	Progressive disease requires at least 1 of the following:
Individual target nodes/nodal masses	Score 4 or 5 with an increase in intensity of uptake from baseline and/or New FDG-avid foci consistent with lymphoma at interim or end-of-treatment assessment	PPD progression An individual node/lesion must be abnormal with: LDi > 1.5 cm and Increase by ≥ 50% from PPD nadir and An increase in LDi or SDi from nadir
Extranodal lesions		

		0.5 cm for lesions $\leq$ 2 cm 1.0 cm for lesions $>$ 2 cm In the setting of splenomegaly, the splenic length must increase by $>$ 50% of the extent of its prior increase beyond baseline (eg, a 15-cm spleen must increase to $>$ 16 cm). If no prior splenomegaly, must increase by at least 2 cm from baseline New or recurrent splenomegaly
	None	New or clear progression of preexisting nonmeasured lesions
Nonmeasured lesion	New FDG-avid foci consistent with lymphoma rather than another etiology (eg, infection, inflammation). If uncertain regarding etiology of new lesions, biopsy or interval scan may be considered	Regrowth of previously resolved lesions A new node $>$ 1.5 cm in any axis A new extranodal site $>$ 1.0 cm in any axis; if $<$ 1.0 cm in any axis, its presence must be unequivocal and must be attributable to lymphoma Assessable disease of any size unequivocally attributable to lymphoma
New lesions	New or recurrent FDG-avid foci	New or recurrent involvement
Bone Marrow

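### Both Cheson 99 response tables carry Lugano PET classes and no CRu row, and part of the first secondary objective (Cheson response before year 3, MRD after ASCT) has no scheduled output

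*SAP*

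**What the plan says.** **Response tables.** SAP 5.7.4 has one Cheson 99 table for the Efficacy Set (numbered 5.7-6) and one for the Safety Set (numbered 5.7-2). Table numbers are reused in section 5.7, so the titles are the safer reference. Both list "Complete Metabolic Response", partial and no metabolic response, "Progressive Metabolic Disease" and not evaluated. Their columns are the 3-year evaluation and end of treatment.

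**Endpoint 1** (SAP 3.2.2.1, Protocol 15.1.2.1) is response after 3 years of maintenance by Cheson 1999. The overall rate is described by naming CR and PR only. SAP 4.5.1 adds: "The number and percent of patients falling into each category of response will be provided".

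**Endpoint 2** (SAP 3.2.2.2) is the 3-year PET result by Lugano 2014. The PET tables in SAP 5.7.5 show whether a scan was done, whether there was a hypermetabolic lesion, SUVmax and site.

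**First secondary objective** (Protocol 6.2, SAP 3.1.2) asks for Cheson response and MRD before ASCT, after ASCT and every 6 months. Protocol 9.6 to 9.8 schedule the corresponding assessments.

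**The concern.** Cheson 1999 and the Lugano PET classes are different systems, and the protocol keeps them apart: at 3 years, Protocol 9.8 lists PET by Lugano and response by Cheson as separate items. A table titled with one system and filled with the other can be completed in two ways. The programmer either enters PET classes under a Cheson title, or enters Cheson classes and decides privately where CRu goes. A patient with a residual mass can then be complete under one choice and not under the other. SAP section 1 says the document exists to pre-specify analyses before database lock, so this choice should be written down.

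The second strand is a gap. Data named in an objective are collected at visits for which no table reports them, so that part of the objective would go unanswered in the planned outputs.

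**Working it through.** The plan states no figure for response rates, so the check is a comparison of texts and a count of outputs.

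**1. Do the classes map one to one?**

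| Cheson 1999 (Protocol Appendix 8) | Row in SAP 5.7.4 | Match |
|---|---|---|
| CR: "All lymph nodes and nodal masses must have regressed to normal size" | Complete metabolic: "Score 1, 2, or 3 with or without a residual mass on 5 Point Scale" | Not equivalent; a residual mass is allowed on PET |
| CRu, for example: "A residual lymph node mass greater than 1.5 cm in greatest transverse diameter that has regressed by more than 75% in the SPD" | None | Missing |
| PR | Partial metabolic | Different criteria, size against uptake |
| SD | No metabolic response | Appendix C groups it under "No Response or stable disease"; mislabelled only |
| PD | Progressive metabolic | Different basis |

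On the last row, Protocol 9.11 says: "Progressive disease should be based on CT scan and not PET or MRD". That sentence governs how progression is determined and not how tables are labelled, so it is context here and carries no weight of its own.

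The SAP uses Cheson classes with a CRu row in two other places: response after relapse treatment (Table 5.88-4, section 5.8) and disease status at death (Table 5.10-6, section 5.10.4). The right template already exists.

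**2. Does the placing of CRu change the overall rate?** Overall response counts everyone in CR or PR. If CRu is counted with CR, or with PR, the total is the same and only the split moves. The total falls only if CRu is counted as neither.

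**3. Cheson times in the objective, to year 3.** Later Cheson assessments are yearly, so the count stops there. Columns are counted by their titles.
- After induction, before ASCT (Protocol 9.6): 1
- After ASCT (Protocol 9.7): 1
- Every 6 months for 3 years (Protocol 9.8): 6
- Total: 1 + 1 + 6 = 8
- With a scheduled column: month 36 = 1
- Without: 1 + 1 + 5 (months 6, 12, 18, 24, 30) = 7

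**4. MRD times in the objective, to year 3.**
- Before ASCT: covered in marrow (SAP 5.7.1)
- After ASCT: sampled in blood and marrow (Protocol 9.7), no table of status
- Months 6 to 36: 6 times, covered in blood (SAP 5.6.3); month 36 also in marrow (SAP 5.7.6)
- Total: 1 + 1 + 6 = 8, of which 7 are covered and 1 is not

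**5. Could another planned output fill the gap?** The primary criterion analysis (SAP 4.2, Protocol 15.5) lists the primary criterion, exposure, stem cell collection failure and safety. Neither Cheson response nor MRD after ASCT is among them. MRD after ASCT can enter time to first negative result and duration of negativity (SAP 5.7.7), but no status at that visit is tabulated. Marrow involvement after ASCT (Table 5.6-2) is not MRD.

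**6. Is the design touched?** No. The exact binomial for 46 of 70 gives a one-sided alpha of 0.0452 at 55% and power of 0.820 at 70%, as planned, and uses none of these tables.

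**The case against.** **The labels are a template slip that any programmer would correct.** Probably so in origin, and for stable disease the slip is harmless. It does not settle CRu, which has no row to be relabelled. Endpoint 2 also does not prescribe which rows a PET table must have. Still, it rests on Lugano criteria, and the only Lugano classes in the response shells stand under a Cheson title.

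**CRu is plainly a response, so the overall rate is safe.** This largely stands. The protocol synopsis and sections 10.2.2 and 10.2.3 list CRu beside CR and PR (with stable disease) as grounds to go on to transplant or maintenance. Protocol 5.4 names PR, CR and CRu together. Appendix 8 defines relapse jointly for CR and CRu, and its CRu threshold of more than 75% regression exceeds the 50% required for PR. A reader might infer from the CR and PR wording that CRu drops out of the overall rate, at 1/70 = 1.4 points per patient in the planned Efficacy Set. The documents do not favour that reading and do not give the number of CRu patients.

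**The shells follow the endpoint text.** Correct. The same definition stands in Protocol 15.1.2.1 and SAP 3.2.2.1. The mismatch is between objective and endpoint within both documents; the SAP has not departed from the protocol.

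**Earlier responses appear elsewhere.** In part. The end-of-treatment column shows Cheson response before year 3 for patients who stopped early. PET after induction and after ASCT, abnormal CT in maintenance and timing of progression are also reported. None of these gives Cheson response at the objective's scheduled times.

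**PET classes could not fill the end-of-treatment column.** A reader might infer this because the Protocol Appendix 3 schedule shows no PET there. It is not a safe argument: Protocol 9.9 allows any baseline procedure to be repeated for response, and the SAP's PET tables have an end-of-treatment column.

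**Conclusion.** The point holds in two parts. First, both Cheson 99 tables have the wrong row labels and no place for CRu, and the PET tables lack the Lugano class. The split between CR and PR is therefore undefined. The effect on that split cannot be sized, because the documents give no count of CRu patients. The overall rate does not change as long as CRu is counted as response.

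Second, the first secondary objective is only partly served: 7 of 8 Cheson times and 1 of 8 MRD times up to year 3 have no scheduled output. The Cheson count takes the 3-year column at its title. The same rows should not also be counted as a Lugano output, nor should Lugano be called wholly absent from the SAP.

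These are secondary, descriptive results. The primary test, the 46/70 rule, PFS and OS are unaffected. The change should be made before the final tables are produced.

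**What to change.** 1. In both response tables of SAP 5.7.4, use the rows CR, CRu, PR, SD, PD and not evaluated. State that overall response is CR+CRu+PR.
2. Put the Lugano classes in the PET tables of SAP 5.7.5 at 3 years.
3. Reconcile the objective (Protocol 6.2, SAP 3.1.2) with the endpoint text (Protocol 15.1.2.1, SAP 3.2.2.1).
4. Add descriptive columns for Cheson response after induction, after ASCT and at months 6, 12, 18, 24 and 30, and for MRD after ASCT in marrow and blood.
5. In each new column show the number assessed and the number missing, and state the denominator. SAP 4.5.1 bases percentages on non-missing data and SAP 4.6 excludes imputation, whereas endpoints 1 and 3 count missing as non-response or MRD positive. Those two rules were written for the 3-year and on-demand times. They should not be extended automatically to patients who were never transplanted.
6. In the same edit, settle the interval level: these shells print 95%, while SAP 4.5.1 sets 90% for response rates.

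**Cost.** Items 1, 2 and 6 are shell edits. Items 3 to 5 add table columns and need a protocol clarification or a documented SAP departure, because both documents share the endpoint text. No new assessment is needed.

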**Table 5.7-2 Response according to Cheson 99 – Safety Set**

	Evaluation after 3 years of maintenance N=XX	End of treatment N=XX
Response (Cheson 99)		
Complete Metabolic Response	XX (XX.X%)	XX (XX.X%)
Partial Metabolic Response	XX (XX.X%)	XX (XX.X%)
No Metabolic Response	XX (XX.X%)	XX (XX.X%)
Progressive Metabolic Disease	XX (XX.X%)	XX (XX.X%)
Not Evaluated	XX (XX.X%)	XX (XX.X%)
Overall Response Rate (ORR)		
Patients with ORR	XX (XX.X%)	XX (XX.X%)
IC 95%	[XX.X% - XX.X%]	[XX.X% - XX.X%]
Overall Response Rate* (ORR)		
Patients with ORR	XX (XX.X%)	XX (XX.X%)
IC 95%	[XX.X% - XX.X%]	[XX.X% - XX.X%]

\* Patients who relapsed or died during treatment phase are considered as non-responders even if they were responders before withdrawal.

## 5.7.5 PET results

**Table 5.7-7 PET scan result – Efficacy Set**

	After Induction N=XX	After ASCT N=XX	After 3 years of maintenance N=XX	End of Treatment N=XX
PET scan				
No	XX (XX.X%)	XX (XX.X%)	XX (XX.X%)	XX (XX.X%)
Yes	XX (XX.X%)	XX (XX.X%)	XX (XX.X%)	XX (XX.X%)
If done, hypermetabolic lesion				
No	XX (XX.X%)	XX (XX.X%)	XX (XX.X%)	XX (XX.X%)
Yes	XX (XX.X%)	XX (XX.X%)	XX (XX.X%)	XX (XX.X%)
If yes, SUV Max tumoral				
N	XX	XX	XX	XX
Missing	XX	XX	XX	XX
Mean (SD)	XX.X (XX.XX)	XX.X (XX.XX)	XX.X (XX.XX)	XX.X (XX.XX)
Median	XX.X	XX.X	XX.X	XX.X
Q1 ; Q3	XX ; XX	XX ; XX	XX ; XX	XX ; XX
Min ; Max	XX ; XX	XX ; XX	XX ; XX	XX ; XX
If yes, localisation				
XXX	XX (XX.X%)	XX (XX.X%)	XX (XX.X%)	XX (XX.X%)
XXX	XX (XX.X%)	XX (XX.X%)	XX (XX.X%)	XX (XX.X%)

**Table 5.7-2 PET scan result – Safety Set**

	After Induction N=XX	After ASCT N=XX	After 3 years of maintenance N=XX	End of Treatment N=XX
PET scan				
No	XX (XX.X%)	XX (XX.X%)	XX (XX.X%)	XX (XX.X%)
Yes	XX (XX.X%)	XX (XX.X%)	XX (XX.X%)	XX (XX.X%)
If done, hypermetabolic lesion				
No	XX (XX.X%)	XX (XX.X%)	XX (XX.X%)	XX (XX.X%)
Yes	XX (XX.X%)	XX (XX.X%)	XX (XX.X%)	XX (XX.X%)
If yes, SUV Max tumoral				
N	XX	XX	XX	XX
Missing	XX	XX	XX	XX
Mean (SD)	XX.X (XX.XX)	XX.X (XX.XX)	XX.X (XX.XX)	XX.X (XX.XX)
Median	XX.X	XX.X	XX.X	XX.X
Q1 ; Q3	XX ; XX	XX ; XX	XX ; XX	XX ; XX
Min ; Max	XX ; XX	XX ; XX	XX ; XX	XX ; XX
If yes, localisation				
XXX	XX (XX.X%)	XX (XX.X%)	XX (XX.X%)	XX (XX.X%)
XXX	XX (XX.X%)	XX (XX.X%)	XX (XX.X%)	XX (XX.X%)

## 5.7.6 MRD results

**Table 5.7.6-1** MRD results according to ddPCR on BM – Efficacy Set

	After 36M of maintenance N=XX	After 36M of maintenance on-demand N=XX	End of treatment N=XX
MRD results on BM			
Negative	XX (XX.X%)	XX (XX.X%)	XX (XX.X%)
Positive	XX (XX.X%)	XX (XX.X%)	XX (XX.X%)
Missing	XX (XX.X%)	XX (XX.X%)	XX (XX.X%)

## 5.7.7 Duration of MRD negativity

**Table 5.7.7** Events since first MRD negativity – Efficacy Set

	Efficacy Set N=XX
Patients with MRD negativity	XX
If yes, time to first negative MRD	
N	XX
Missing	XX
Mean (SD)	XX.X (XX.XX)
Median	XX.X
Q1 ; Q3	XX ; XX
Min ; Max	XX ; XX
Event according to MRD negativity duration	
No	XX (XX.X%)
Yes	XX (XX.X%)

Duration of MRD negativity is defined as the time from the date of attainment the first negative MRD to the date of positive MRD.

For patients achieving a negative MRD but who have not positive MRD or not MRD assessment at the time of analysis, duration of MRD negativity will be censored on the date of last MRD assessment.

**Figure 5.7.7** Duration of MRD negativity – Efficacy Set

**Table 5.7.7** Duration of MRD negativity – Efficacy Set – Survival Estimates

## 5.7.8 Stem cell collection failure

**Table 5.7.3.2-1** Description of stem cell collection failure – Safety Set

	Safety Set N=XX
Leukapheresis	
Done	XX (XX.X%)
Not Done	XX (XX.X%)
If not done, specify the reason:	
Progression	XX (XX.X%)
Collection failure	XX (XX.X%)
Toxicity	XX (XX.X%)
Other	XX
If collection failure, specify:	
Sepsis	XX (XX.X%)
Not enough cells	XX (XX.X%)
Logistical problem	XX (XX.X%)
Other cause	XX
If done, Total collected cells CD34+	
N	XX
Missing	XX
Mean (SD)	XX.X (XX.XX)
Median	XX.X
Q1 ; Q3	XX ; XX
Min ; Max	XX ; XX

## 5.8 Progression / Relapse

**Table 5.88-1 Summary of progression/relapse – Safety Set**

	Safety Set N=XX
Patients who progressed/relapsed	
No	XX (XX.X%)
Yes	XX (XX.X%)
If yes, time since inclusion (months)	
N	XX
Missing	XX
Mean (SD)	XX.X (XX.XX)
Median	XX.X
Q1 ; Q3	XX ; XX
Min ; Max	XX ; XX

**Table 5.88-2 Involvement at progression/relapse – Safety Set**

	Safety Set N=XX
Progression/Relapse	XX
Initial Involvement	
No	XX (XX.X%)
Yes	XX (XX.X%)
New Involvement	
No	XX (XX.X%)
Yes	XX (XX.X%)
Nodal Involvement	
No	XX (XX.X%)
Yes	XX (XX.X%)
Extra-nodal Involvement	
No	XX (XX.X%)
Yes	XX (XX.X%)

**Table 5.88-3 Treatment for progression/relapse – Safety Set**

	Safety Set N=XX
Progression/relapse	XX
Progression/relapse treatment	
No	XX (XX.X%)
Yes	XX (XX.X%)
If yes,	
Monoclonal antibody	
No	XX (XX.X%)
Yes	XX (XX.X%)
Other immunotherapy	
No	XX (XX.X%)
Yes	XX (XX.X%)
If yes, ibrutinib	
Yes	XX (XX.X%)
No	XX (XX.X%)
Chemotherapy	
No	XX (XX.X%)
Yes	XX (XX.X%)
Radiotherapy	
No	XX (XX.X%)
Yes	XX (XX.X%)
Autologous transplant	
No	XX (XX.X%)
Yes	XX (XX.X%)
Allogenic transplant	
No	XX (XX.X%)
Yes	XX (XX.X%)
If yes, allograft transplant	
Yes	XX (XX.X%)
No	XX (XX.X%)
IMiD	
No	XX (XX.X%)
Yes	XX (XX.X%)

Epigenetic modifiers agents		
No		XX (XX.X%)
Yes		XX (XX.X%)
Kinase inhibitor		
No		XX (XX.X%)
Yes		XX (XX.X%)
Other anti-cancer therapy		
No		XX (XX.X%)
Yes		XX (XX.X%)

